**Figure 1 Study design**

### 2.1 Overview of study procedures

**Table 1 Study flow chart: Screening to day 180 after imlifidase infusion**

Study visit	1	2	3	4	5	6	7	8	9	10	11	12
Day	-28-0	0-2	3-6	7	9	14	21	28	64	90	120	180
Assessment /Time window	Screening			+/- 1 d	+2 d	+/- 2 d	+/- 3 d	+/- 3 d	+/- 7 d	+/- 7d	+/- 14 d	+/- 14 d
Informed Consent	X											
Demographics and medical/surgical history	X	X										
Inclusion/exclusion	X	X										
Physical examination	X											X

Weight	X	X				X						
Height	X											
Vital signs	X	X		X c				X		X	X	X
Body temperature	X	X										
CDC and FACS	X	X a										
DSAs	X	X		X c		X	X	X	X	X	X	X
Pregnancy test (serum)	X	X h										X
Sperm sample	X k											
Adverse events		X	X	X	X	X	X	X	X	X	X	X
ECG	X											X
Drug infusion		X										
Safety laboratory tests	X	X		X c		X	X	X	X	X	X	X
HIV and hepatitis	X											
P-creatinine (eGFR)		X		X c		X	X	X	X	X	X	X
Proteinuria						X		X	X	X	X	X
U-protein electrophoresis		X d	X d	X d	X d							
PK sampling		X	X f	X c	X g	X						
PD sampling (IgG)		X		X b	X g	X	X	X	X			X l
ImmunoCAP IgG (ADA)		X		X b		X	X	X	X	X	X	X
ImmunoCAP IgE	X											
Virus screen (BK-, EBV, CMV-PCR)	X					X		X	X	X		
Methylprednisolone Loratadine		X										
Rituximab					X e							
High dose IVIg				X i								
Kidney biopsy		X j										X
Check concomitant medication	X	X	X	X	X	X	X	X	X	X	X	X

Day 0 is the imlifidase dosing day

a For LD patients the screening crossmatch test must be repeated pre-dose

b PD (IgG) and ADA samples will be taken pre- and postdose IVIg on day 7

c This assessment will be done prior to IVIg infusion

d 24 hour urine collections for protein electrophoresis will be performed daily until day 9

e Rituximab can be given day 9-11 if a longer time window is required for practical reasons

f PK will be drawn at 96 hours ±4h

g PD (IgG) and PK samples will be drawn prior to Rituximab infusion on day 9-11

h If a female patient has been hospitalized between screening visit and visit 2, a pregnancy test at screening visit will suffice and a pregnancy test at visit 2 is not required

i If deemed necessary by the investigator this dose may be split into two doses administered over days 6-8

j A biopsy will be performed on the donor graft prior to transplantation (for DD transplantations)

k Precautionary sperm sample on patient's request (applicable only for France)

l PD sample at visit 12 was removed on January 18, 2018 (Amendment 8)

**Table 2 Study flow chart from 0 (pre-dose) to 48 h after imlifidase infusion. Time-points after dosing (0) relates to start of infusion**

Study visit	2					
	0/ Pre-dose	Dosing	2h	6h	24h	48 h
Assessment /Time window	≤ 60 min	0	+/- 15 min	+/- 30 min	+/- 2h	+/- 2h
Demographics and medical/surgical history	X					
Inclusion/exclusion criteria	X					
Weight	X					
Vital signs (BP & pulse respiratory frequency)	X		X	X	X	X
Body temperature	X		X	X	X	X
CDC and FACS CXM	X		X	X	X	
DSAs	X		X	X	X	X
Pregnancy test (serum)	X c					
Adverse events	X	X	X	X	X	X
Drug infusion		X				
Safety laboratory tests	X		X	X	X	X
P-creatinin, eGFR					X	X
U-protein electrophoresis					X b	X b
PK sampling	X		X	X	X	X
PD sampling (IgG)	X		X	X	X	X
ImmunoCAP IgG (ADA)	X					X
Methylprednisolone Loratidine a	X					
Check concomitant medication	X		X	X	X	X

Assessments will be repeated from the pre-dose timepoint if a second dose of imlifidase is given

aPremedication with methylprednisolone and loratadine will be repeated before the second imlifidase dose

b24 hour urine collections for protein electrophoresis will be performed daily until day 9

cIf a female patient has been hospitalized between screening visit and visit 2 a pregnancy test at screening visit will suffice and a pregnancy test at visit 2 is not required

## 2.2 Determination of sample size

Sample size is not based on formal statistical considerations. Due to the nature of the primary endpoint of the study it is expected that data from 15-20 patients should suffice to achieve the objectives of the study. Also, the sample size is in line with experience from previous similar phase II studies with other compounds to obtain adequate safety, tolerability and PK data to achieve the objectives of the study.

## 2.3 Blinding

The study is open-label.

## 2.4 Data pre-processing

### Data sets

The export data sets from the [REDACTED] data management database will be transformed into SDTM structure and format following the implementation guide version 3.2 (current version) and also following “Therapeutic Area Data Standards User Guide for Kidney Transplant Version 1.0 (Provisional)”. ADaM data sets will be prepared based on the SDTM data sets following implementation guide version 1.1 (current version). Tables, figures and listings will be prepared from the ADaM data sets.

### Derivation of pharmacokinetic parameters

PK analysis of the serum concentration data for imlifidase will be performed at Hansa Medical. The actual sampling times will be used in the parameter calculations. Concentration-time raw data and PK parameters will be calculated for each individual as well as reported per received dose(s).

In earlier clinical studies with imlifidase an open 2-compartment model was found to best describe the data. The model can be described by model parameters V (volume of central compartment), K21, Alpha and Beta. A similar approach will be applied to this study and non-compartmental parameters can be calculated from these model parameters as secondary parameters by standard PK equations, including where possible: the area under the curve to infinite time (AUC), the terminal half-life (T1/2), clearance (CL), volume of distribution at steady-state (Vss) and volume of distribution during the elimination phase (Vz). In addition, Cmax and Tmax may be obtained directly from the experimental data.

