ECG	X											X
Drug infusion		X										
Safety laboratory	X	X		X ^c		X	X	X	X	X	X	X
HIV and hepatitis	X											
P-creatinin, (eGFR)		X		X ^c		X	X	X	X	X	X	X
Proteinuria						X		X	X	X	X	X
U-protein electrophoresis		X ^d	X ^d	X ^d	X ^d							
PK sampling		X	X ^f	X ^c	X ^g	X						
PD sampling (IgG)		X		X ^b	X ^g	X	X	X	X			X
ImmunoCAP IgG (ADA)		X		X ^b		X	X	X	X	X	X	X
ImmunoCAP IgE	X											
Virus screen (BK-, EBV, CMV-PCR)	X					X		X	X	X		
Methylprednisolone Loratadine		X										
Rituximab					X ^e							
High dose IVIg				X ⁱ								
Kidney biopsy		X ^j										X

Check concomitant medication	X	X	X	X	X	X	X	X	X	X	X	X
------------------------------	---	---	---	---	---	---	---	---	---	---	---	---

Day 0 is the IdeS dosing day

^aFor LD patients the screening crossmatch test must be repeated pre-dose

^bPD (IgG) and ADA samples will be taken pre- and post-dose IVIg on day 7

^cThis assessment will be done prior to IVIg infusion

^d24 hour urine collections for protein electrophoresis will be performed daily until day 9

^eRituximab can be given day 9-11 if a longer time window is required for practical reasons

^fPK will be drawn at 96 hours ±4h

^gPD (IgG) and PK samples will be drawn prior to Rituximab infusion on day 9-11

^hIf a female patient has been hospitalized between screening visit and visit 2, a pregnancy test at screening visit will suffice and a pregnancy test at visit 2 is not required

ⁱIf deemed necessary by the investigator this dose may be split into two doses administered over days 6-8

^ja biopsy will be performed on the donor graft prior to transplantation (for DD transplantations)

Table 2. Study flow chart: 0/Pre-dose to 48 h after IdeS infusion. Time-points after dosing (0) relates to START of infusion.

Study visit	2					
	0/ Pre-dose	Dosing	2h	6h	24h	48 h
Assessment /Time window	≤60 min	0	+/- 15 min	+/- 30 min	+/- 2h	+/- 2h
Demographics and medical/surgical history	X					
Inclusion/exclusion criteria	X					
Weight	X					
Vital signs (BP & pulse respiratory frequency)	X		X	X	X	X
Body temperature	X		X	X	X	X
CDC and FACS CXM	X		X	X	X	
DSAs	X		X	X	X	X
Pregnancy test (serum)	X ^c					
Adverse events	X	X	X	X	X	X
Drug infusion		X				
Safety laboratory tests	X		X	X	X	X
P-creatinin, eGFR					X	X
U-protein electrophoresis					X ^b	X ^b
PK sampling	X		X	X	X	X
PD sampling (IgG)	X		X	X	X	X
ImmunoCAP IgG (ADA)	X					X
Methylprednisolone Loratadine ^a	X					
Check concomitant medication	X		X	X	X	X

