6.1.4 Administration of investigational drug

Intravenous IdeS will be administered over at least 15 minutes. The first 3 patients will receive one dose of 0.25 mg/kg BW IdeS on study day 0. If it is considered safe and the desired effect is not achieved (negative crossmatch test) after the first dose, an additional IdeS infusion can be given within 2 days of the first infusion. The dose schedule may be increased to 0.5 mg/kg BW given once or twice after the first 3 patients have been tested. The decision to escalate the dose will be done after evaluation of safety and efficacy as described in section 4.2.

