Patients found eligible at the screening visit will be included in the study. At visit 2 the eligibility check will be repeated within 60 min from IdeS dosing. A pregnancy test will be taken. If a female patient has been hospitalized between screening visit and visit 2, a pregnancy test at screening visit will suffice and a pregnancy test at visit 2 is not required. In addition methylprednisolone and loratadine will be administered predose to prevent infusion reactions. Vital signs, body temperature, safety laboratory sampling, pharmacokinetic and pharmacodynamics sampling will be performed pre-dose, 2 h, 6 h, 24 h and 48 h post IdeS infusion. In addition blood sampling for DSAs will be drawn at pre-dose, 2 h, 6 h, 24 and 48 h. Blood sampling for CDC- and FACS-CXM will be done at pre-dose, 2 h, 6 h, and 24 h. Any effort should be made to obtain crossmatch test for all time-points indicated in the study flowcharts. If this is not possible due to logistics on specific sites, the sponsor can allow a smaller number of time-points to be evaluated. However, as a minimum one crossmatch test pre-dose and one post-dose IdeS must be performed to allow evaluation of the primary endpoint. ADA will be sampled at pre-dose and 48 h post IdeS infusion. P-creatinine will be measured at 24 h and 48 h post IdeS infusion and eGFR will be calculated. Repeat 24 hour urine collections will be performed day 1-9 for urine protein electrophoresis analysis. AEs and concomitant medication will be recorded in the CRF throughout the visit. AEs that occur in the time period prior to administration of the study drug should be recorded as part of the patient's medical history but will not be considered a treatment emergent adverse event (TEAE) unless directly related to study procedures (e.g. hematoma secondary to laboratory testing) or it meets the definition of an SAE. A kidney biopsy on the donor kidney will be performed in deceased donor patients.

Visit 3 (day 3-6)

Twenty-four- (24)-hour urine collections will be performed daily, day 1-9, for urine protein electrophoresis analysis. AE and concomitant medication will be assessed. PK will be drawn at 96 hours \pm 4h.

Visit 4 (day 7)

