## List of abbreviations and definition of terms

ADA	Anti-drug antibody
ADaM	Analysis data model
AE	Adverse event
AUC	Area under the concentration versus time curve
BMI	Body mass index
BP	Blood pressure
CDC	Complement dependent cytotoxicity
C max	Maximum observed concentration
CRF	Case report form
CV	Coefficient of variation
DSA	Donor specific antibodies, anti-human leukocyte antigen (HLA) donor-specific antibodies
ECG	Electrocardiogram
FACS	Fluorescence-activated cell sorting
IMP	Investigational medicinal product
LD	Living donor
LLOQ	Lower limit of quantification
MedDRA	Medical Dictionary for Regulatory Activities
NCA	Non compartmental analysis
PD	Pharmacodynamics
PK	Pharmacokinetics
PP	Per-protocol analysis set
PRA	Panel reactive antibody
PT	Preferred term
SAB-HLA	Single antigen beads - human leukocyte antigen
SAE	Serious adverse event
SAP	Statistical analysis plan
SAS	Safety analysis set
SD	Standard deviation
SE	Standard error
SOC	System organ class
SDDM	Study data tabulation model
T ½	Elimination half-life
TEAE	Treatment emergent adverse event
TLF	Tables, listings and figures
T max	Time of observed C max

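### Observed Cmax and Tmax for imlifidase are limited by a first post-dose sample at 2 h and should not be tabulated as peak parameters without saying so

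*SAP*

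**What the plan says.** **Infusion.** Protocol 6.1.4: "Intravenous IdeS will be administered over at least 15 minutes". No upper limit is given.

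**Sampling.** Protocol 6.2, visit 2: "pharmacokinetic and pharmacodynamics sampling will be performed pre-dose, 2 h, 6 h, 24 h and 48 h post IdeS infusion". The caption of the detailed flow chart fixes the clock. The protocol (Table 2, section 4.1) has "Time-points after dosing (0) relates to START of infusion", and the SAP (Table 2, section 2.1) has "Time-points after dosing (0) relates to start of infusion". The 2 h sample has a window of ± 15 min. After 48 h the next PK sample is the one described by "PK will be drawn at 96 hours ±4h", followed by days 7, 9 and 14. A note to Table 2 repeats the assessments from pre-dose if a second dose is given.

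**Parameters.** SAP 2.4 reports that in earlier studies "an open 2-compartment model was found to best describe the data". It plans the same approach here, calculating AUC, terminal half-life, CL, Vss and Vz from the fitted model. Cmax and Tmax are treated differently: they "may be obtained directly from the experimental data". Protocol 11.1 says the same. The SAP's abbreviation list defines Cmax as "Maximum observed concentration" and Tmax as the time of that observation. SAP 4.4.2 tabulates the PK parameters and summarises concentrations by time point. Neither document plans a sample at the end of infusion, defines a model-predicted peak, or labels the observed maximum as limited by the schedule.

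**The concern.** With a constant-rate intravenous infusion the concentration peaks when the infusion stops. If the first sample comes well after that, the observed Tmax says when blood was first drawn and nothing about the drug. The observed Cmax is the level after some distribution and elimination have already taken place. In a two-compartment drug the decline is steepest just after the infusion, which is the unsampled interval here.

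The PK profile up to day 14 is a secondary endpoint. A table entry named Cmax is normally read as peak exposure. A reader who sets it beside a Cmax from a study with an end-of-infusion sample would be comparing different quantities. A Tmax of about 2 h in nearly every patient could likewise be taken for a property of imlifidase.

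**Working it through.** The plan states no figure on this point, so there is none to reproduce. The check has two parts.

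**1. Timing (document inputs only)**

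- Shortest infusion: T = 15 min = 0.25 h (protocol 6.1.4).
- First post-dose sample: 2 h, window 1.75 to 2.25 h, from start of infusion (Table 2 in both documents).
- Gap from the end of a 15-minute infusion to the first sample: 2 − 0.25 = 1.75 h (1.5 to 2.0 h with the window).
- Observed Tmax over true Tmax: 2/0.25 = 8 (1.75/0.25 = 7 to 2.25/0.25 = 9).

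In a linear two-compartment model the concentration rises during the infusion and only falls afterwards. If the infusion ends before the first sample, that sample is the highest one, whatever the rate constants. Evaluating the model at 2, 6, 24, 48, 96, 168, 216 and 336 h, for infusions of 0.25 to 2 h and all the constants below, put the maximum at 2 h every time.

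Protocol 6.2 words the times as after the infusion. If the clock ran from the end of infusion, the gap would be longer still: 2 h instead of 1.75 h. The flow-chart captions are explicit, so start of infusion is used here.

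**2. Size of the Cmax shortfall (needs assumptions)**

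The documents give no rate constants. Assumed: early (alpha) half-life 0.5 to 8 h; late (beta) half-life 24 or 96 h; alpha share f of the bolus response 0, 50% or 80%.

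For t ≥ T, with k = ln 2 / half-life, the concentration is, up to a constant,

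C(t) = f · g(kα) · exp(−kα(t − T)) + (1 − f) · g(kβ) · exp(−kβ(t − T)), where g(k) = (1 − exp(−kT)) / (kT).

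The quantity of interest is C(2)/C(T), observed over true peak.

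Worked case: T = 0.25 h, f = 0.5, alpha half-life 2 h, beta half-life 24 h.

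- kα = 0.3466 and kβ = 0.02888 per hour; g = 0.9579 and 0.9964.
- C(T) = 0.5 × 0.9579 + 0.5 × 0.9964 = 0.977.
- Over 1.75 h the two terms are multiplied by 0.5453 and 0.9507, so C(2) = 0.5 × 0.9579 × 0.5453 + 0.5 × 0.9964 × 0.9507 = 0.735.
- Ratio 0.735/0.977 = 0.752, a shortfall of about 25%.

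Range of C(2)/C(T) over all assumed half-lives, at the nominal 2 h sample:

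| Infusion | f = 0 | f = 50% | f = 80% |
|---|---|---|---|
| 0.25 h | 0.951–0.987 | 0.555–0.924 | 0.285–0.885 |
| 0.5 h | 0.958–0.989 | 0.607–0.934 | 0.338–0.901 |
| 1 h | 0.972–0.993 | 0.716–0.956 | 0.476–0.933 |
| 2 h | 1.000 | 1.000 | 1.000 |

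For a 15-minute infusion the shortfall runs from about 1% (ratio 0.987) to about 71% (ratio 0.285).

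**The case against.** **The size is unknown and may be small.** This stands. A reader might use a single-phase decay over 1.75 h, 1 − 2^(−1.75/t), and infer a loss of 70%, 46%, 26% or 14% for early half-lives t of 1, 2, 4 or 8 h. The documents do not support those figures. They put the whole decline in the early phase, whereas the SAP names a two-compartment model. With half the response in the early phase and a late half-life of 24 h, the same half-lives give about 36%, 25%, 15% and 10%. Fifteen minutes is also only a minimum, and a longer infusion shrinks the loss.

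**The SAP is permissive and already calls the values observed.** Also true. Reporting is optional, and the definition does not claim an end-of-infusion peak. But if the parameters are tabulated, nothing tells the reader that the first possible observation was at about 2 h.

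**Much is already transparent.** Concentrations are summarised by time point, all data are listed, and actual sampling times enter the calculations. This limits the harm, since the 2 h level appears under its own label. Using actual times does not create an earlier sample, however.

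**A model peak is no better.** In part this stands: no sample before 2 h informs the early phase, so a predicted peak depends on the model shape. It can be an addition with a label, not a plain replacement.

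**The harm is conjectural.** A reader might infer that a safety-margin comparison is compromised. The visible text plans no comparison of Cmax with any margin; the NOAEL statement in protocol 2.6 concerns doses and is partly redacted. The risk is misreading of a table.

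**Conclusion.** The point holds as a reporting defect in two descriptive PK parameters. For any infusion that ends before the first sample, observed Tmax is fixed by the schedule and observed Cmax is below the end-of-infusion peak. This rests only on the documented sampling times and on linear disposition of the kind that the SAP names.

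The size is not established. About 1% to 71% for a 15-minute infusion reflects assumed rate constants. The shortfall is close to none if the infusion lasts about 2 h, counting from its start. The documents therefore do not support saying that the bias is large, or that the PK endpoint as a whole fails. AUC, half-life, CL and the volumes are planned from the model, Cmax is not named in the endpoint, no hypothesis is tested, and the primary endpoint is untouched. The change is worth making because it is cheap and stops a schedule artefact from being tabulated as a PK parameter.

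**What to change.** In SAP 2.4 and in the PK parameter tables:

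1. Report the observed maximum, separately for each dose, as the concentration at the first post-dose sample (about 2 h), and do not call it Cmax. Give the actual sampling time. The split by dose matters because SAP 4.1 records that 3 patients had a second dose.
2. Omit Tmax, or state beside it that the sampling schedule determines it.
3. If a peak is wanted, add the model-predicted concentration at the actual end of infusion, labelled as an extrapolation that no sample before 2 h informs.
4. Record the change against protocol 11.1 in SAP section 5.

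The cost is wording and table labels, since the model is to be fitted anyway; item 3 also needs the recorded infusion times. The price is that no directly observed Cmax is reported, and any model peak depends on the model shape. Moving a sample to the end of infusion is no remedy for this trial, because SAP 4.1 describes dosing as already done.

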### **3 Analysis sets**

The analysis sets will be determined at the data review prior to database lock. Decisions will be documented in the database lock minutes.

#### **3.1 Safety analysis set**

The safety analysis set (SAS) will consist of all patients that received any amount of study medication.

#### **3.2 Per protocol analysis set**

The Per protocol analysis set (PP) will consist of all patients in the safety set that has recorded at least one efficacy endpoint value. Data from patients with one or more major protocol violations are excluded. The PP analysis set will be used for presentation of efficacy, pharmacokinetic, and pharmacodynamic endpoints.

## 4 Statistical analyses and presentation of data

### 4.1 General considerations

No formal statistical hypothesis testing will be performed in this study. All presentation of data will be descriptive by nature. Missing data will in general not be imputed or adjusted for in other ways.

The protocol states that tabulations will be by actual dose received. The protocol allowed for the DSMB to decide on dose escalation. All patients were administered planned dose(s) of 0.25 mg/kg BW. For one patient the actual dose was reduced due to an allergic reaction. For 3 patients the protocol option of administering a 2nd dose was used. Efficacy and safety tabulations will be by number of administrations (1 or 2 doses) and total including all patients. The patient with reduced dose [REDACTED] will be included in the “1 dose” group for safety evaluation but excluded from the PP.

Numerical data will be presented in summary tables by number of patients, arithmetic mean (geometric mean and coefficient of variation [CV] where applicable), median, standard deviation (SD), minimum and maximum. Categorical data will be presented by number and percent of patients as well as number of events (where applicable).

Endpoints will be presented graphically as mean profile plots, individual profile plots and spaghetti plots. The sampling frequency is for efficacy and some safety endpoints high from pre-dose until 48 hours followed by decreasing frequency. Therefore, the graphical presentation will, in most cases, be as box plots with a categorical x-axis. For other data, a plot with linear x-axis (0 to 180 days) may be supplemented with a subset plot where only the first 24 or 48 hours are included on the x-axis.

All data will be listed. Auxiliary database parameters will not be included. Listings will be sorted by patient ID, parameter and time point. In general listings will not be mentioned in detail below.

The study did not include any interim analyses.

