Patients will be closely monitored for all adverse events and the second dose will only be given if the investigator considers it safe after evaluating adverse events and over all patient status after the first IdeS dose. The principal investigator must make sure that sufficient facilities and procedures are available to handle emergency situations during the study. The study sites have extended experience in phase I/II studies within transplantation and graft rejection treatment as well as handling biological drugs. The sites have adequate procedures in place to handle unexpected adverse reactions.

As described above in section 2.4 a phase II study in asymptomatic TTP patients, enrollment was stopped after two subjects showing signs of serum sickness. Previously, 27 patients without concomitant immunosuppression medications have been treated with IdeS and none of them showed signs of serum sickness. The sponsor cannot rule out that the underlying disease was a factor in the development of serum sickness in these two subjects. Based on all available safety information from non-clinical and clinical studies, the overall benefit/risk profile of IdeS still appears favorable.

3 Study objectives

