#### 1.1.2 Endpoints

**The primary endpoint of this study is:**

- Efficacy defined as imlifidase ability to create a negative crossmatch test within 24 hours after imlifidase dosing

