## 2 Study design

This is a phase II, open label exploratory study to assess the imlifidase efficacy in creating a negative crossmatch test (CXM) in a total of 15-20 patients (7-13 with living donors and 7-13 with a deceased donor) who exhibit DSAs and have a positive crossmatch test to their available live donors. The first 3 patients in this study will receive a kidney from a deceased donor. The study will primarily examine the efficacy of imlifidase in creating a negative CXM in patients. Included patients will be treated with imlifidase on day 0. If it is considered safe and the desired effect is not achieved (negative crossmatch) a second dose can be given within 2 days of the first infusion. In addition to imlifidase patients will be given high dose IVIg (2 g/kg BW, maximum of 140 g) on day 7 and anti CD20 (Rituximab) on day 9 as outlined in [Figure 1](#). DSA levels will be monitored 2, 6, 24 and 48 hours and 7, 14, 21, 28, 64, 90, 120 and 180 days after the last imlifidase dosing. Safety, including kidney function will be monitored at multiple time points up to 180 days after treatment. PK, PD and ADA will be followed. For details on assessments see flow chart in [Table 1](#). Patients who are not eligible for transplantation after imlifidase treatment will not be transplanted and thus will not receive any induction therapy or immunosuppression. All patients who receive imlifidase will also be asked to remain in the study and be followed up according to the study protocol even if they are not transplanted. In addition, patients who lose their graft during the course of the study will remain in the study and be followed up according to the study protocol and clinical practice at the respective site.

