## **4.4 Efficacy**

### **4.4.1 Primary efficacy analysis**

The primary efficacy endpoint is defined as imlifidase ability to create a negative crossmatch test within 24 hours after imlifidase dosing. The primary endpoint will be presented for the PP analysis sets.

The planned time points (according to the flowchart) are: Screening, pre-dose, 2h, 6h, 24h, and 48h. In general, only the pre-dose and 24h analyses are performed, while the other planned analyses are missing. For each of the crossmatch tests (FACS B-cell, FACS T-cell, amplified and non-amplified analyses of CDC B-cells and CDC T-cells, and virtual) summary tabulations by time point will be made.

For each patient an overall response is defined as positive if at least one of the assays is positive at pre-dose and all recorded assays are negative at 24h. The overall response is summary tabulated.

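### The crossmatch response rule does not say which dose its pre-dose and 24h samples refer to, and the 1-dose and 2-dose efficacy columns depend partly on the first-dose result

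*SAP*

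**What the plan says.** The primary endpoint in SAP 1.1.2 is the ability to "create a negative crossmatch test within 24 hours after imlifidase dosing". SAP 4.4.1 makes this operational: a patient's overall response "is defined as positive if at least one of the assays is positive at pre-dose and all recorded assays are negative at 24h". Neither sentence gives a dose number. SAP 4.4.1 also reports on the data: "In general, only the pre-dose and 24h analyses are performed, while the other planned analyses are missing".

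Protocol 6.1.4 opens the option of a further infusion within 2 days with the condition "If it is considered safe and the desired effect is not achieved (negative crossmatch test) after the first dose". Protocol 2.6 adds that "the second dose will only be given if the investigator considers it safe after evaluating adverse events". SAP 2 repeats the option. The note under SAP Table 2 reads "Assessments will be repeated from the pre-dose timepoint if a second dose of imlifidase is given", and SAP 4.1 records that three patients received a second dose.

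For presentation, SAP 4.1 states "Efficacy and safety tabulations will be by number of administrations (1 or 2 doses) and total including all patients". For DSA monitoring, SAP 2 does set a clock: the sampling times run to "120 and 180 days after the last imlifidase dosing". It sets none for the crossmatch. SAP 5, on deviations from the protocol analysis, does not mention the matter.

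**The concern.** There are two linked problems.

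First, a re-dosed patient is scheduled for two pre-dose and two 24h crossmatches, and the rule does not say which pair decides response. A patient who was still positive 24 hours after dose 1 and negative 24 hours after dose 2 is a non-responder on one reading and a responder on the other. On the second reading, conversion up to about 48 + 24 = 72 hours after the first infusion counts as within 24 hours. Two programmers could both follow the SAP and report different primary totals.

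Second, the grouping variable is set after baseline and partly by the primary outcome. First-dose failures who are re-dosed leave the 1-dose column and enter the 2-dose column. The 1-dose column therefore does not estimate conversion after a single dose, and the two columns are not dose groups that can be compared. Single-dose conversion is not a named endpoint. But Protocol 2.5 says the sponsor would like a dose that works in every patient when given once, to shorten the time to transplantation, so a reader may well take the 1-dose column as that rate. The SAP text names no summary of first-dose conversion.

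**Working it through.** The plan has no figure to reproduce. The study is descriptive, and Protocol 12.3 and SAP 2.2 say that the sample size has no formal statistical basis. The check is a count.

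**Inputs from the documents**
- Planned patients: 15 to 20 (SAP 2).
- Re-dosed patients: 3 (SAP 4.1).
- One patient with a reduced dose is excluded from the per-protocol set (SAP 4.1).
- The primary endpoint is presented for the per-protocol set (SAP 4.4.1).

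**Assumptions, because the documents do not give these values**
- Per-protocol N = 15 − 1 = 14 to 20 − 1 = 19. Further major violations would lower it.
- All 3 re-dosed patients are in the per-protocol set and are negative after dose 2.
- Every patient is positive at a baseline taken before dose 1.
- r = first-dose failures among the 3 re-dosed (0 to 3); k = failures who were not re-dosed.

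**Effect of the clock on the total**
- First-dose clock: (N − r − k)/N.
- Last-dose clock: (N − k)/N.
- Difference: r/N, whatever k is.

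| r | N = 14 | N = 19 |
|---|---|---|
| 0 | 0 | 0 |
| 1 | 1/14 = 7.1 points | 1/19 = 5.3 points |
| 2 | 2/14 = 14.3 points | 2/19 = 10.5 points |
| 3 | 3/14 = 21.4 points | 3/19 = 15.8 points |

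With r = 3 and k = 0, the first-dose clock gives 11/14 = 78.6% (exact 95% CI 49.2 to 95.3) or 16/19 = 84.2% (60.4 to 96.6). The last-dose clock gives 14/14 = 100% (76.8 to 100) or 19/19 = 100% (82.4 to 100). In the 2-dose column the same choice moves the result from 0/3 to 3/3.

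**The 1-dose column against first-dose conversion over all patients**

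The 1-dose column is (N − 3 − k)/(N − 3). Subtract (N − r − k)/N:

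| r | k | N = 14 | N = 19 |
|---|---|---|---|
| 3 | 0 | 11/11 − 11/14 = +21.4 | 16/16 − 16/19 = +15.8 |
| 3 | 2 | 9/11 − 9/14 = +17.5 | 14/16 − 14/19 = +13.8 |
| 0 | 0 | 0 | 0 |
| 0 | 2 | 9/11 − 12/14 = −3.9 | 14/16 − 17/19 = −2.0 |

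The column overstates single-dose conversion when the re-dosed patients were first-dose failures, which is the stated reason for re-dosing. Otherwise the gap can be nil or slightly negative.

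**The case against.** The grouping has a reason. Protocol 12.2.1 asks for presentation by actual dose received, and all planned doses were 0.25 mg/kg, so the number of administrations was the main difference left. The SAP does no testing, shows a total, never compares the columns and never calls the 1-dose column a single-dose rate. All of this stands. No error rate is affected, and the column problem by itself needs only a footnote. It does not settle the clock, because a descriptive proportion still needs a defined numerator and the total is the figure that the clock changes.

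Three stronger readings are tempting, and the documents do not support them.
- A reader might infer that the plan inflates the primary result. The reasons for re-dosing the three patients, their crossmatch results and the per-protocol size are not given, and the effect can be zero.
- A reader might infer that first-dose results are lost. SAP 4.4.1 says that the pre-dose and 24h tests are the ones generally performed, and SAP 4.4.2 stresses gaps between them, which on the schedule are 2h and 6h. If dose 2 came after 24 hours, the dose-1 24h sample may exist, and a further sample is scheduled before dose 2. Crossmatch data and number of doses are listed by patient. The documents do not say when dose 2 was given.
- A reader might infer that baseline could be reset at dose 2, so that a patient with no positive assay at that point could never count as a responder. This is remote. Such a patient would fall outside the stated reason for re-dosing, and Protocol 6.1.4 places the first dose on day 0, which favours a baseline before dose 1. It does not settle the 24h clock.

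The table shells might separate the time points by dose. SAP 7 and 8 place them in separate documents, and SAP 8 says that the templates may change after signature. They cannot be checked here, and the primary definition belongs in the SAP.

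**Conclusion.** The point holds and should be fixed, though it does not undermine the study. The SAP does not name the reference dose for its primary response rule, and nothing else in the two documents supplies it. At most three patients are affected. The total can differ by r/N: from nothing to 15.8 points (N = 19) or 21.4 points (N = 14). The upper figures require that all three re-dosed patients failed dose 1, converted after dose 2 and are in the per-protocol set. They illustrate the range and do not estimate what happened.

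The 1-dose and 2-dose efficacy columns depend partly on outcome. They depend only partly, because re-dosing is optional and also needs a safety judgement. The 1-dose column should not be read as single-dose conversion or set against the 2-dose column.

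**What to change.** In SAP 4.4.1, take baseline before the first dose for every patient, and report two labelled rows with all per-protocol patients in the denominator.

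- **Row (a), first-dose response:** all recorded assays negative at the 24h sample after dose 1, taken before any second dose. A patient whose last crossmatch before dose 2 was positive, or who was re-dosed for a recorded positive crossmatch, is a non-responder whatever earlier samples showed. A re-dosed patient with neither a crossmatch between doses nor a recorded reason for re-dosing is not evaluable, stays in the denominator as not shown to respond, and is counted separately.
- **Row (b), response after up to two doses:** all recorded assays negative at the 24h sample after the last dose.

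State which row is the primary result. Footnote the 1-dose and 2-dose efficacy columns as outcome-dependent and not for comparison. Keep that grouping for safety. Exact confidence intervals are optional.

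The cost is a few sentences in the SAP, one extra table row and a footnote. Row (a) needs an inter-dose crossmatch or a recorded reason for re-dosing; at most three patients could lack both. The downside is that a possibly lower first-dose figure is shown.
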